3.4 Study procedure

3.4.1 Diagnosis and Pre-treatment evaluation – Visit 1

Patients eligible for screening will be informed about this study as soon as they are being scheduled for TURB. Pre-treatment evaluation at Visit 1 will only be performed after the patient has agreed to participate and has signed and dated the informed consent form. No treatment will be initiated before informed consent has been given. Pre-treatment evaluation will be performed based on the study inclusion and exclusion criteria, including:

- Patient informed consent
- Demographics
- Medical history (including previous treatment for NMIBC)
- Urinalysis (including culture)
- Urine cytology
- Upper tract imaging: CT, IVU, MRI or US

The investigator/research nurse will complete a screening log of all patients who were approached to participate in the trial. This log contains the patients' initials, date of birth and date of visit. If the patient fails to enter the study, the reason(s) for not participating or non-eligibility will be documented.

If the patient enters the study, anticoagulation medication must be interrupted before surgery according to the protocol of the hospital. Anticoagulation medication may be re-continued after surgery according to hospital protocol.

3.4.2 Treatment with TURB – Visit 2

Following successful completion of the pre-treatment evaluation, patients will continue into the second visit. This consecutive visit may ideally be combined with Visit 1 and should at the latest take place within 14 days after Visit 1. This visit consists of the surgical procedure, and thus will include:

- Limited physical examination
- Examination of vital signs
- Recording of concomitant medication
- Assessment of bladder symptoms prior to TURB
- SPIES or WLI only assisted TURB

Peri-operative complications will be recorded when appropriate, up to 30 days of hospitalization. In addition, hospital stay and duration of operation will be recorded. When appropriate, (serious) adverse events ([S]AEs) will be recorded.

3.4.3 First follow up – three months after surgery – Visit 3

At three months after surgery, all patients will undergo a routine follow up using WLI cystoscopy. A two-week window will be allowed for the timing of this examination. All visible lesions should be confirmed histologically. Adjuvant treatment will be offered according to the local protocols. When appropriate, information on re-TUR and/or adjuvant treatment will be recorded, as well as adverse events. Information on re-TUR includes reasons for performing this procedure to determine if it was an incomplete resection or a true recurrence found at follow up. Information on adjuvant treatment includes type, timings, time limits and dose.

3.4.4 Intermediate follow up – 6, 9, 12, 18, 24 and 30 months after surgery – Visit 4 to 9

At the time points specified above, all patients will undergo a follow up using WLI cystoscopy. A four-week window will be allowed for the timing of this examination. All visible lesions should be confirmed histologically.

3.4.5 Last study follow up – three years after surgery – Visit 10

At three years after surgery, all patients will undergo a follow up using WLI cystoscopy. A four-week window will be allowed for the timing of this examination. All visible lesions should be confirmed histologically.

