2. OBJECTIVES

Primary Objective:

1. To compare the recurrence rate of tumor at 12 months following SPIES assisted TURB (Arm A) with White Light Imaging only assisted TURB (Arm B) in patients with primary or recurrent non-muscle-invasive urothelial bladder cancer (NMIBC Ta/T1/CIS). A subgroup analysis will be carried out for patients presenting with only primary tumors.

Secondary Objectives:

1. To assess the recurrence rate of tumor at short and long term follow up (3 months and 3 years) after SPIES or WLI assisted TURB in patients with NMIBC.
2. To assess the peri-operative morbidity (30 days) between SPIES and WLI assisted TURB by comparing the proportion of adverse events and using the Clavien-Dindo score.

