2.1 Study design

This study is a multicenter randomized controlled trial in which the recurrence rates of cancer between SPIES assisted and WLI assisted TURB are compared. Randomization is stratified by tumor multiplicity (single or multiple), tumor status (primary or recurrent) and macroscopic findings (papillary or flat, where CIS is scored as flat lesion). Patients randomized into the experimental arm (Arm A) will undergo SPIES and WLI assisted TURB, whereas the patients in the control arm (Arm B) will undergo WLI only assisted TURB. WLI is chosen as control, since it is considered the gold standard for detecting bladder tumors. Short and long term follow up will be recorded in order to evaluate the health gains for patients over a longer period. Perioperative (30 days) complications will be compared between the two treatment arms to evaluate the safety of SPIES.

Each participating center must submit this protocol to their local MEC and each participating center is responsible for the insurance of their patients. Data from all participating centers will be collected through electronic Case Report Forms (eCRFs), with use of an online Data Management System (DMS), which is located and maintained at the CROES office.

Members of the CROES office will perform all analyses. Each center willing to participate should have enough experience and be familiar with SPIES. A center is considered to have enough experience when a minimum of 10-20 procedures have already been done with SPIES prior to including patients in this study.

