3.1.2 Secondary study parameters/endpoints

- Peri-operative morbidity (30 days) assessed by the Clavien-Dindo score
- Proportion of re-TUR (defined as within 3 months of initial TURB: this can be a planned TURBT because of resection of high risk tumor, or because of recurrent tumor confirmed at cystoscopy at three months)

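### Section 3.4.2 ties the recording of complications to the hospital stay, while the safety endpoint is 30-day morbidity; events after discharge are left to passive or late capture

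*Protocol*

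**What the plan says.** Three places in the protocol define the safety comparison, and none mentions the hospital stay:

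- Section 2 (Objectives), second secondary objective: "To assess the peri-operative morbidity (30 days) between SPIES and WLI assisted TURB by comparing the proportion of adverse events and using the Clavien-Dindo score".
- Section 2.1 (Study design): "Perioperative (30 days) complications will be compared between the two treatment arms to evaluate the safety of SPIES".
- Section 3.1.2 (Secondary endpoints): "Peri-operative morbidity (30 days) assessed by the Clavien-Dindo score".

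Section 3.4.2 (Visit 2) gives the recording rule: "Peri-operative complications will be recorded when appropriate, up to 30 days of hospitalization". The same paragraph goes on: "In addition, hospital stay and duration of operation will be recorded". It ends with a sentence that carries no hospital limit: "When appropriate, (serious) adverse events ([S]AEs) will be recorded".

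The next scheduled contact is Visit 3, in section 3.4.3: "At three months after surgery, all patients will undergo a routine follow up using WLI cystoscopy". A two-week window applies, and adverse events are among the items to be recorded there when appropriate. No visit or call is scheduled at day 30.

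Section 4.2.1 defines adverse events over the whole study and requires recording of all that are volunteered by the patient or observed by staff. Section 4.2.2 counts any event that requires hospitalisation as serious, to be reported to the sponsor within 24 hours.

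**The concern.** The endpoint needs the same 30 days of observation for every patient. Section 3.4.2 is the only procedural rule that sets a 30-day window for complications. As worded, it treats 30 days as a cap on an inpatient stay, so the period in which complications are actively recorded ends when the patient goes home. Length of stay is itself a recorded variable, so the protocol expects it to differ between patients.

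Two consequences follow if centers apply the sentence as written. First, complications after discharge that do not lead to readmission may be under-counted in both arms. That shrinks the absolute difference between arms and favours a finding of no difference. Second, if stays differed between arms, ascertainment would differ with them. Section 2.1 gives this comparison the task of evaluating the safety of SPIES, so a finding of no difference should not arise from incomplete capture. Section 3.4.9 foresees 15 centers, which may read the sentence differently.

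**Working it through.** **1. The passages side by side**

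| Place | Window | In-hospital limit? |
|---|---|---|
| Section 2, secondary objective 2 | 30 days | No |
| Section 2.1 | 30 days | No |
| Section 3.1.2 | 30 days, Clavien-Dindo | No |
| Section 3.4.2, complications | 30 days of hospital stay | Yes, read literally |
| Section 3.4.2, (S)AEs | None stated | No |
| Section 3.4.3, Visit 3 | Three months, two-week window | No |
| Section 4.2.1 | Whole study; volunteered or observed | No |
| Section 4.2.2 | Hospitalisation makes an event serious | No |

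The fourth row conflicts with the first three. The last four rows give events after discharge a route into the data. None of those four asks for a Clavien-Dindo grade or for ascertainment up to day 30. For an event without readmission, capture depends on the patient volunteering it or recalling it about two months after day 30.

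**2. Size: illustration only**

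The protocol states no complication rate, length of stay or timing of complications, so there is no figure of its own to reproduce. Every clinical input below is an assumption.

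Let p be the true 30-day rate, s the share of events after discharge, and c the fraction of those that are captured. Then

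recorded rate = p × (1 − s + s × c).

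For p from 5% to 15% and s from 25% to 75%:

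| Capture after discharge | Lowest recorded rate | Highest recorded rate |
|---|---|---|
| c = 0 | 0.05 × 0.25 = 1.3% | 0.15 × 0.75 = 11.3% |
| c = 0.5 | 0.05 × 0.625 = 3.1% | 0.15 × 0.875 = 13.1% |
| c = 1 | 5% | 15% |

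**3. Effect on power**

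Inputs: 1,928 / 2 = 964 per arm (section 2.5), all assumed evaluable; two-sided 5% level and continuity-corrected test, as in section 2.5; assumed true rates 14% versus 10%; assumed s = 0.5.

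With d the difference in rates and p̄ their mean, the continuity-corrected effective size is n′ = (n − 1/d)² / n, and

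power = Φ{[d√n′ − 1.96 √(2p̄(1 − p̄))] / √(p₁(1 − p₁) + p₂(1 − p₂))}.

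| c | Recorded rates | d | n′ | Value in braces | Power |
|---|---|---|---|---|---|
| 1 | 14% vs 10% | 0.04 | (964 − 25)² / 964 = 914.6 | 0.674 | 75.0% |
| 0.5 | 10.5% vs 7.5% | 0.03 | (964 − 33.3)² / 964 = 898.5 | 0.262 | 60.3% |
| 0 | 7% vs 5% | 0.02 | (964 − 50)² / 964 = 866.6 | −0.207 | 41.8% |

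**4. Effect of unequal stays**

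Take equal true rates of 10%, with 40% of events before discharge in one arm and 60% in the other (assumed). In-hospital capture alone would show 0.10 × 0.4 = 4% versus 0.10 × 0.6 = 6%. With half of the later events captured, it would show 0.10 × (0.4 + 0.5 × 0.6) = 7% versus 0.10 × (0.6 + 0.5 × 0.4) = 8%.

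**The case against.** **Post-discharge events do have a route.** A reader might infer from 3.4.2 that complications are recorded only in hospital and that everything after discharge is lost. The protocol does not support that. Section 4.2.1 requires recording of all volunteered or observed adverse events during the study, 4.2.2 makes readmissions reportable, 3.4.3 provides for adverse events at Visit 3, and the last sentence of 3.4.2 has no hospital limit. The objective in section 2 also uses the proportion of adverse events as one of its two measures, so part of the endpoint does not rest on the restricted sentence. This stands, and it rules out zero capture as the plan's intention. It does not make capture active or uniform up to day 30.

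**The phrase may be loose wording.** With a plain 30-day window stated three times, the author may have meant 30 days from surgery or admission. That is possible, but the sentence does not say it, and the correction is needed on either reading.

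**The numbers are assumed.** This is correct. The protocol sets no power target for this endpoint, and the 42% figure requires that no post-discharge event is captured. It is the end of a range, not an estimate.

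**Nothing suggests that stays differ between arms.** Also correct: both arms undergo TURB, section 8.1 expects no added risk with SPIES, and length of stay is recorded, so a difference would be visible. Bias between arms is a possibility, not a demonstrated effect.

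**The eCRF is not shown.** It may already hold dated, graded complication fields, so their absence cannot be asserted. The conflict in the protocol text remains.

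**Conclusion.** The point holds as an internal inconsistency in data capture. The window in 3.4.2, read literally, ends at discharge and does not match the 30-day endpoint in sections 2, 2.1 and 3.1.2. General adverse event and SAE reporting covers part of the gap, probably most of the readmissions. Complications up to day 30 without readmission remain open to under-counting, and their ascertainment may vary with length of stay.

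The size of the loss cannot be derived from the protocol. On the assumed 14% versus 10% with half of events after discharge, power runs from 75% (full capture) through about 60% (half of the later events captured) to 42% (none captured). A reader might take 42% as the expected power, but it contradicts the reporting routes that the protocol does provide.

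The change should be made, but this is a secondary safety endpoint. The primary endpoint and the sample size are unaffected.

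**What to change.** 1. Reword 3.4.2 so that all complications within 30 days after TURB are recorded, in hospital or after discharge, each with its date and Clavien-Dindo grade. This also fixes the start of the window.
2. At the existing Visit 3, add a required question, asked identically in both arms, on complications, readmissions and re-interventions between TURB and day 30.
3. Compare the arms on that fixed 30-day window.

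The cost is one reworded sentence and one required item at a visit that already takes place. The downside is slight recall error, because events up to day 30 are asked about at three months. The change concerns data capture only and leaves clinical management as it is.

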3.4.6 Biopsies and histology

Transurethral resection biopsies will be obtained from all flat lesions and suspicious areas. All papillary lesions must be resected completely. Tissue from the resected lesion(s) will be collected for histological assessment. The findings from both biopsies as well as resected lesions will be registered on a bladder chart and will include presence of lesion, size (defined as the diameter of the largest side of the tumor), type (papillary or flat), number of lesions and location (bladder neck anterior/posterior, trigone, around ureteric orifice right/left, posterior wall, right/left lateral wall, anterior wall, dome). The local pathologist will examine the samples. Staging of the tumors will be done according to the TNM 2009 classification

(Babjuk et al., 2013). Both WHO grading systems will be used for the report (2004 and 1973). For consistency, a standardized pathology procedure will be used to perform the analysis.

3.4.7 Concomitant medication

Any licensed concomitant medication required for the well-being of the patient is permitted. Anti-coagulation medication must be discontinued during surgery according to local protocol, but may be continued after the procedure. Concomitant medication usage will be documented at any visit during this trial.

3.4.8 Study duration (patient)

Patients participating in this study will undergo a screening visit, followed by SPIES or WLI assisted TURB. During TURB, cystoscopy will be performed and biopsies and resections will be taken for analysis. Several follow up visits will be planned (at three, six, nine and twelve months and 18, 24, 30 and 36 months after TURB) to check for possible recurrence of the tumors. Depending on the grade and stage of the (initial or recurrent) tumors, these visits could be scheduled more often if the treating physician deems necessary.

3.4.9 Study duration (investigator)

The number of centers participating in this study is 15. Each center is expected to recruit 100 patients a year. With the required number of patients being 1928, the estimated recruitment time is approximately one and a half year. Due to the maximum follow up of three years, the total study duration is expected to be four and a half years.

3.5 Surgery procedures

At Visit 2, as described in the preceding paragraphs, patients will undergo TURB. The procedure for TURB is described in this paragraph, for patients in both treatment Arm A and Arm B.

The following procedure will be utilized to accomplish the cystoscopic examination of each patient:

For patients allocated to treatment Arm A (SPIES):

1. Turn on the white light. Inspection of the bladder and indicating all papillary lesions and flat and suspicious lesions seen on a bladder diagram.

2. Turn to the SPIES software image. Inspection of the bladder and indicating all papillary lesions and flat and suspicious lesions seen on a bladder diagram (Appendix A). The choice of SPIES-platform (i.e. Clara, Chroma, Spectra A or Spectra B) is to the discretion of the investigator, and will be recorded. The use of the SPIES-VIEW mode, which provides two images at the same time (WL and SPIES) on the same screen, is allowed and is to the discretion of the investigator.
3. Perform complete resection (TURB) of all papillary lesions, and obtain biopsies of all flat lesions and suspicious areas. Choice of modality (SPIES or WL) for resection is to the discretion of the investigator, and will be recorded.

For patients allocated to treatment Arm B (WLI):

1. Turn on the white light. Inspection of the bladder and indicating all papillary lesions and flat and suspicious lesion seen on a bladder diagram (Appendix A).
2. Perform complete resection (TURB) of all papillary lesions, and obtain biopsies of all flat lesions and suspicious areas.
3. The patient will be treated to normal hospital routines

All positive or suspect areas will be resected or biopsied using WL or SPIES. All papillary lesions must be resected completely.

Adjuvant treatment is up to the local investigator, however we recommend standardization for low-, intermediate, and high-risk groups (as defined by EORTC).

3.6 Withdrawal of individual subjects

Subjects can leave the study at any time for any reason if they wish to do so without any consequences and without providing reason(s) for withdrawal and without prejudices to further treatment. Completion or trial termination for any reason will be fully documented in the eCRF. The investigator can decide to withdraw a subject from the study for urgent medical reasons, which should be documented.

3.7 Follow-up of subjects withdrawn from trial

Subjects who are withdrawn from the study will be followed and checked according to the Good Clinical Practice (GCP) Guidelines for clinical trials.

4. SAFETY REPORTING

4.1 Section 10 WMO event

In accordance to section 10, subsection 1, of the WMO, the investigator will inform the subjects and the reviewing accredited MEC if anything occurs, on the basis of which it appears that the disadvantages of participation may be significantly greater than was foreseen in the research proposal. The study will be suspended pending further review by the accredited MEC, except insofar as suspension would jeopardize the subjects' health. The investigator will take care that all subjects are kept informed.

4.2 AEs, SAEs

4.2.1 Adverse events

Adverse events are defined as any undesirable experience occurring to a subject during the study, whether or not considered related to the experimental intervention. All adverse events reported spontaneously by the subject or observed by the investigator or his/her staff will be recorded.

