3.3 Randomisation and treatment allocation

Patients presenting with a bladder cancer and who are scheduled for TURB or patients who are scheduled for random biopsies and/or TURB because of a bladder wash out or voided urine with malignant (G3) cells will be included in the study. Eligible patients who are willing to participate will be randomized in a ratio of 1:1 to either Arm A (SPIES+WLI assisted TURB) or Arm B (WLI assisted TURB). The CROES will utilize the randomization to minimize systematic error and potential selection bias by the investigators. The randomization will be performed by using randomly permuted blocks (computer generated), with block size of 6. To assure balanced characteristics and comparable prognosis between the two arms, the

randomization will be stratified on tumor multiplicity (single or multiple), tumor status (primary or recurrence) and macroscopic findings at time of baseline visit (papillary or solid/flat tumor [including CIS]), leading to 8 stratification groups.

Concealment of treatment allocation is achieved by: 1) reducing the time between randomization and intervention, 2) first deciding whether the patient meets all study entry criteria, and 3) if so, randomize the patient in the DMS. The randomization will take place just before the intervention starts; ideally both occur on the same day. The DMS performs the randomization then reveals treatment allocation. The patients will be blinded to their allocation. Due to the nature of the procedure, the surgeon will not be blinded.

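### The 30-day adverse-event comparison relies on passive collection with no study contact between TURB and three months, so non-serious events after discharge are likely to be missed and a real difference diluted

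*Protocol*

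**What the plan says.** Secondary objective 2 (section 2) assesses 30-day peri-operative morbidity between the arms "by comparing the proportion of adverse events and using the Clavien-Dindo score". Section 3.1.2 lists the matching endpoint: "Peri-operative morbidity (30 days) assessed by the Clavien-Dindo score". Section 2.1 gives its purpose: "Perioperative (30 days) complications will be compared between the two treatment arms to evaluate the safety of SPIES".

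Collection is described in four places.
- Section 4.2.1: "All adverse events reported spontaneously by the subject or observed by the investigator or his/her staff will be recorded".
- Section 3.4.2 (Visit 2, the TURB): "Peri-operative complications will be recorded when appropriate, up to 30 days of hospitalization".
- Section 3.4.3 (Visit 3, three months after surgery, two-week window): "When appropriate, information on re-TUR and/or adjuvant treatment will be recorded, as well as adverse events".
- Section 3.2 records complications during surgery, and section 4.2.2 requires serious events to reach the sponsor within 24 hours.

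On blinding, section 3.3 states: "The patients will be blinded to their allocation. Due to the nature of the procedure, the surgeon will not be blinded". It does not say whether ward, clinic or research staff know the allocation.

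**The concern.** A between-arm comparison of event proportions needs every patient to have the same chance of having an event recorded. Under 4.2.1 an event enters the data if the patient volunteers it or someone notices it. The protocol describes no common set of questions, and no scheduled contact falls inside the 30-day window once the patient has gone home. A discharged patient who was never asked then looks the same as one who had no complication.

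The protocol expects no additional risk from SPIES (sections 8.1 and 8.2), and this comparison is where the trial would test that expectation. Equal under-recording in both arms pushes the result towards no difference, which would read as reassurance. An analysis plan cannot repair this later, because events that were never elicited are not in the database.

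**Working it through.** **Text check.** Recording provisions by type of event:
- During surgery: recorded under 3.2, whatever the patient reports.
- In hospital: recorded under 3.4.2, when appropriate.
- Serious, at any time: reported under 4.2.2.
- Non-serious, after discharge, up to day 30: only the general rule in 4.2.1, and whatever emerges at Visit 3 under 3.4.3. From day 30 to three months (about day 90) is roughly 60 days.

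The gap is in the last group.

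**Inputs for the size of the effect.**
- From section 2.5: total 1,928 at 1:1, so 1,928 / 2 = 964 per arm; two-sided 5%. This sample size was set for recurrence. The protocol gives no figure for the adverse-event comparison, so there is none to reproduce.
- Assumed: true 30-day event proportions of 15% and 10%; capture c of 100%, 75% or 50%, equal in both arms; no event recorded that did not occur.

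**Dilution.** Recorded proportion = true proportion × c. Power is found by enumerating both binomials with the pooled two-proportion z-test. As a check, power ≈ Φ[(d − 1.96·s0)/s1], where d is the recorded difference, s0 = √(2·p̄(1−p̄)/964) with p̄ the mean of the two proportions, and s1 = √([p1(1−p1) + p2(1−p2)]/964).

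| Capture | Recorded | d | (d − 1.96·s0)/s1 | Check | Enumeration |
|---|---|---|---|---|---|
| 100% | 15.0% v 10.0% | 5.0 points | (0.0500 − 0.0295)/0.0150 = 1.36 | 0.914 | 0.916 |
| 75% | 11.25% v 7.5% | 3.75 points | (0.0375 − 0.0260)/0.0132 = 0.87 | 0.807 | 0.810 |
| 50% | 7.5% v 5.0% | 2.5 points | (0.0250 − 0.0216)/0.0110 = 0.31 | 0.621 | 0.623 |

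**Unequal capture.** This applies only if capture differs by arm. With equal true rates of 10%, capture of 60% v 50% records 6.0% v 5.0%, and the chance of p < 0.05 is 0.162. Capture of 65% v 50% records 6.5% v 5.0%, and the chance is 0.294. With equal capture and equal true rates (for example 5.0% v 5.0% recorded), the same enumeration gives 0.051, so no false difference arises. The unequal cases apply the gap to all events, although blinded patients supply some of them, so they overstate what the observed route alone would do.

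**The case against.** A reader might infer that, because the surgeon knows the arm, the adverse-event comparison is biased by arm and may show a difference that is not there. The documents do not support that as a general claim.
- Section 3.3 blinds the patients. While that holds, what they volunteer cannot depend on knowing the arm, so under-reporting by this route dilutes a difference but does not create one.
- Only the surgeon is stated to be unblinded. To say that staff in general know the allocation goes beyond the text.
- The comparison does not rest on 4.2.1 alone. Sections 3.2, 3.4.2 and 4.2.2 separately provide for intra-operative, in-hospital and serious events, so the more severe events depend less on a patient speaking up.

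Three further points can be made for the plan. The eCRF is not shown and might contain a fixed complication item. The phrase about recording when appropriate may simply mean if an event occurred. Section 4.2.1 sets a duty to record and does not forbid asking. The event rates and capture proportions are also assumptions, and the trial was not sized for this endpoint.

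The points on blinding and on the other recording routes stand, and they limit the bias argument to events observed or graded by the surgeon, or by staff whose blinding is not stated. The remaining points do not remove the dilution argument. It needs no unblinding, and a site that follows the written protocol exactly would have no instruction to ask a discharged patient anything before three months.

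**Conclusion.** The point holds as a weakness in measurement. As written, the plan is likely to under-capture non-serious events between discharge and day 30, and this weakens a stated safety comparison. With assumed true rates of 15% v 10% and 964 per arm, power falls from 92% to 81% at 75% capture and to 62% at 50% capture. The actual loss cannot be derived from the protocol, which gives neither a complication rate nor a capture rate.

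A false difference is possible but confined to the observed and graded route. The 16% and 29% figures show what unequal capture would do if it occurred; nothing in the protocol shows that it will. The effect is limited to a secondary safety endpoint and the primary recurrence endpoint is untouched. The change should be made, but the trial's main conclusion does not depend on it.

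**What to change.** In sections 4.2.1 and 3.4.3:
- Keep spontaneous, observed, intra-operative and serious-event recording as they are.
- Add one short list of post-TURB complications covering days 0 to 30, each item answered yes or no with a date. Ask it of every patient in both arms at discharge and at the existing Visit 3, preferably by someone other than the operating surgeon.
- Grade every event from any source by Clavien-Dindo, and base the 30-day comparison on all sources combined. Patient answers alone would not do: patients cannot report intra-operative events they were not told of, and those who die or miss Visit 3 give no answers there.

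The cost is one eCRF page at contacts that already take place, with no extra visit or test. There are two downsides. More minor events will be recorded, so reported morbidity rises in both arms. Answers at Visit 3 also carry about two months of recall after day 30; this is imperfect but the same in both arms.
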